Review of inclusion/exclusion criteria **	X				>		
C-SSRS	X			X	X		
Review concomitant medications	X	X	Х	х	X	X	X
Vital signs ^b	X	X	X	X	X		
Clinical labs ^c	X	X	X	X	X		
12-lead ECG	X	X	X	X	X		
Urinalysis	X	7		X	X		
Urine pregnancy screen for post-menarchal females	X		> >	X X			
Urine drug screen	X			X	X		
Physical examination ^d	X	X	X	X	X		
Hyperphagia Questionnaire for Clinical Trial (HQ-CT)				X	X		
Dosing with Cannabidiol Oral Solution	X	X	X	X	Xe	X e	
Drug accountability	X	X	X	X	X	X	
AEs	X	X	X	X	X	X	X

ASSESSMENTS	SAFETY PERIOD					TAPER PERIOD	FOLLOW-UP PERIOD ^g
Visit Number 1 ^a		2, 3, 4 (monthly)	5, 6 (quarterly)	7 (End of Study)	Early Withdrawal 8		9 (Phone Call)
Study Time Points	Day 1	Weeks 4, 8, 12	Weeks 24, 36	Week 48		0-6 Days	30 Days After EOS
Visit Window (Days)	± 5	± 5	± 5	± 3		± 3	± 5
End of Study				X	X ^f		

^{**} To be completed prior to enrollment into LTS, specifically within the 2-week period that is allotted post completion of Visit 10 (Study Completion) of INS011-16-085.

AE = adverse event.

^a For patients who enroll within the first 2 weeks after completion of Visit 10 (Study Completion) of INS011-16-085 protocol.

^b Vital signs will be taken after a 5-minute seated rest.

^c If the total bilirubin laboratory value is abnormal, direct bilirubin will be drawn.

^d The physical examination will include weight, and evaluation of general appearance, skin, eyes, ears, nose, throat, neck, lymph nodes, chest, heart, abdomen, and extremities.

^e Following the Safety Period or if the patient withdraws early, the patient will enter a Taper Period. Patients will be tapered off of Cannabidiol Oral Solution as follows: 40 mg/kg/day will be reduced to 30 mg/kg/day for three days, then discontinued; 30 mg/kg/day will be reduced to 20 mg/kg/day for three days, then discontinued. This can be modified by the investigator based upon the patient's response.

f If the patient withdraws prematurely from the Safety Period, all Visit 7 (End of Study) procedures should be conducted. Site staff will follow up with the patient 4 weeks after completion of treatment via the telephone to collect information regarding AEs and concomitant medications.

Follow-up Period Visit 9 will be a phone call.

TABLE OF CONTENTS

PROTOC	COL APPROVAL PAGE	2
PROTOC	COL SYNOPSIS	3
TABLE 0	OF CONTENTS	10
List of Ta	ables	14
List of Fi	gures	14
LIST OF	ABBREVIATIONS AND DEFINITIONS OF TERMS	15
1.	INTRODUCTION	18
1.1.	Cannabidiol	18
1.1.1.	Mechanism of Action	19

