1.6. Summary of Potential Risks and Benefits

As reviewed in Sections 1.2 and 1.3, numerous nonclinical and clinical studies have examined other formulations of CBD. Several areas of potential concern have been identified with the use of CBD, especially in nonclinical studies. These include:

• Competitive binding of CYP proteins (thus, an impact on drug metabolism in the liver). Cannabidiol is metabolized predominantly by CYP3A4 and CYP 2C19. Cannabidiol may inhibit these two isozymes, as well as having small effects on CYP3A5, CYP2D6, CYP1A1, and CYP2C9.

• Potential downregulation of immune responses involving the T, B, T-helper, and T cytotoxic subsets of leukocytes and/or those dependent on IL-2 or IFN-γ.

Based on recent studies of cannabinoid administration in humans, controlled CBD may be safe in humans and animals. While further studies are needed to clarify these reported *in vitro* and *in vivo* side-effects (Braut-Boucher et al., 1986), no infection-related events have been reported in recent studies in the pediatric seizure population.

The inclusion/exclusion criteria, concomitant medication guidelines, and safety monitoring (AEs, clinical laboratory, vital signs, ECG, and physical examination assessments) planned for this study are intended to minimize these potential safety risks.

Criteria for removal of subjects from the study and stopping rules will dictate discontinuation of subject participation should a safety issue arise (see Section 3.3 and Section 3.5, respectively).

The appetite behavior classified as hyperphagia in Prader-Willi Syndrome is the most life threatening (Dykens et al., 2007; Griggs et al., 2015) and until recently, no patient lived over the age of 50 years due to morbid obesity and the related complications (Aycan et al., 2014). The mortality rate in patients with PWS is six times higher than patients with other intellectual disabilities (Einfeld and Kavanagh, 2006) and mortality in patients not treated with growth hormone was estimated to be 3% per year between the ages of 6 and 56 years compared to the general population mortality of 0.13% below 55 years; mortality in Prader-Willi Syndrome below 5 years of age has not been determined (Eiholzer, 2005).

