3.5. Stopping Rules

The Investigator reserves the right to terminate the study in the interest of patient safety and welfare. The Sponsor reserves the right to terminate the study at any time for administrative reasons. Patients will also be discontinued when their liver enzymes and serum bilirubin reach:

- ALT or AST $> 8 \times ULN$.
- ALT or AST > 5 x ULN for more than 2 weeks.
- ALT or AST > 3 x ULN and (TU>2 x ULN or INR>1.5).
- ALT or AST > 3 x ULN with appearance of fatigue, nausea, vomiting, right upper quadrant pain or tenderness, fever, rash, and/or eosinophilia (> 5%).

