6.1.4. Clinical Laboratory Assessments

Blood samples for hematology and chemistry assessments and urine sample for urinalysis will be collected during Visit 1 (Day 1), all monthly & quarterly visits, and Visit 7 (End of Study) or Early Withdrawal.

- Hematology: hemoglobin, hematocrit, total and differential leukocyte count, red blood cell (RBC), and platelet count.
- Chemistry: albumin, blood urea nitrogen (BUN), creatinine, total bilirubin, alkaline phosphatase (ALP), aspartate transaminase (AST), alanine transaminase (ALT), sodium (Na⁺), potassium (K⁺), chloride (Cl⁻), lactate dehydrogenase (LDH), uric acid, glucose, and calcium.
- Urinalysis (Visit 1 and Visit 7 or Early Withdrawal only): pH, specific gravity, protein, glucose, ketones, bilirubin, blood, nitrite, leukocyte esterase, and urobilinogen. If protein, occult blood, nitrite, or leukocyte esterase values are out of range a microscopic examination will be performed.

A urine drug screen (amphetamines, barbiturates, benzodiazepines, cocaine, opiates, phencyclidine, and tetrahydrocannabinol) will be performed during at Visit 1 and Visit 7 (End of Study) or Early Withdrawal.

A urine dipstick pregnancy test will be performed on all female post-menarchal patients during at Visit 1 and Visit 7 (End of Study) or Early Withdrawal.

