7.1. Safety Period

7.1.1. Visit 1 (Day 1)

The following procedures and assessments will be performed:

- Obtain written informed consent/assent (if appropriate).
- Review of inclusion and exclusion assessment.
- Review/assess concomitant medications.
- Record vital signs (seated blood pressure, pulse rate, temperature, and respiration rate).
- Collect blood samples for clinical labs (chemistry and hematology)
- Collect urine sample for urinalysis, urine drug screen, and urine dipstick pregnancy test (all female patients of childbearing potential).
- Perform resting 12-lead ECG.
- Perform physical examinations.
- Record weight.
- Dispense CBD.
- Perform drug accountability.
- Review AEs.

7.1.2. Monthly (Visits 2, 3, and 4) and Quarterly (Visits 5, and 6) Visits

The following procedures and assessments will be performed:

- Review/assess concomitant medications.
- Record vital signs (seated blood pressure, pulse rate, temperature, and respiration rate).
- Collect blood samples for clinical labs (chemistry and hematology)
- Perform resting 12-lead ECG.

- Perform physical examinations.
- Record weight.
- Collect/review/dispense CBD.
- Perform drug accountability.
- Review AEs.

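### The mandatory liver stopping rule uses INR, which no visit or reflex test supplies, and a 2-week ALT/AST persistence limit to which no repeat draw is timed

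*Protocol*

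**What the plan says.** Protocol 3.5 introduces the liver criteria as obligatory: "Patients will also be discontinued when their liver enzymes and serum bilirubin reach" one of four thresholds. Two of them matter here. One is a persistence criterion, "ALT or AST > 5 x ULN for more than 2 weeks". The other is a combined criterion, "ALT or AST > 3 x ULN and (TU>2 x ULN or INR>1.5". I read TU as total bilirubin, because the lead-in sentence refers to serum bilirubin. The remaining two are ALT/AST above 8x ULN, and ALT/AST above 3x ULN with listed symptoms or eosinophils above 5%.

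Protocol 1.6 relies on these rules as a safeguard: "Criteria for removal of subjects from the study and stopping rules will dictate discontinuation of subject participation should a safety issue arise".

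On measurement, the chemistry list in Protocol 6.1.4 begins "Chemistry: albumin, blood urea nitrogen (BUN), creatinine, total bilirubin, alkaline phosphatase (ALP), aspartate transaminase (AST), alanine transaminase (ALT" and goes on to electrolytes and other routine analytes. Hematology covers blood counts, including the leukocyte differential. The visit procedures in Protocol 7.1 and 7.2 take the same two kinds of blood sample: "Collect blood samples for clinical labs (chemistry and hematology". The only reflex test related to the liver is note c to Table 1, repeated in SAP Appendix A: "If the total bilirubin laboratory value is abnormal, direct bilirubin will be drawn".

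**The concern.** A rule that obliges discontinuation needs the measurements that trigger it. INR is named in Protocol 3.5 and nowhere else in either document. The persistence criterion needs a second ALT/AST value soon after two weeks, and nothing asks for one. Whether and when these two triggers are reached therefore depends partly on what each site decides to test, so sites could apply the same written rule differently. At stake is a patient who has reached a mandatory stop and stays on drug until the next visit because the stop has not been detected.

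**Working it through.** The plan states no figure on this point to reproduce. The check has two parts.

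**1. Trace each element of the rule to a required measurement.**

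- ALT/AST above 8x ULN: chemistry at every scheduled visit. Assessable.
- ALT/AST above 3x ULN with a symptom or eosinophils above 5%: adverse event review and the leukocyte differential at every visit. Assessable.
- ALT/AST above 3x ULN with bilirubin above 2x ULN: total bilirubin is in the chemistry panel. Assessable.
- ALT/AST above 3x ULN with INR above 1.5: INR is absent from the panels in Protocol 6.1.4, the procedures in 7.1 and 7.2, note c of Table 1, the analyte table in SAP 6.7.3.1 and SAP Appendix A. Not assessable from required data.
- ALT/AST above 5x ULN for more than 2 weeks: assessable only from two draws. The second required draw is the next scheduled visit.

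The INR branch alone therefore decides the outcome only for a patient with ALT/AST above 3x and up to 8x ULN, bilirubin not above 2x ULN, no listed symptom, eosinophils not above 5%, and INR above 1.5.

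**2. Compare the draw spacing with the 14-day limit.**

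Inputs: draws at Day 1 and Weeks 4, 8, 12, 24, 36 and 48 (Protocol Table 1). Windows are ±5 days, and ±3 days at Week 48. SAP 5.1 defines Day 1 as the date of enrollment, so I treat Day 1 as fixed.

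Formulas: nominal gap = 7 × weeks between draws. Range = nominal gap minus and plus the sum of the two visit windows. Delay = gap − 14. The clock starts at the draw that first shows a value above 5x ULN, and two consecutive scheduled values above 5x count as persistence.

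| Draws | Nominal gap (days) | Range (days) | Delay past limit (days) |
|---|---|---|---|
| Day 1 to Week 4 | 4×7 = 28 | 28−5 = 23 to 28+5 = 33 | 14 (9 to 19) |
| Weeks 4 to 8, 8 to 12 | 28 | 28−10 = 18 to 28+10 = 38 | 14 (4 to 24) |
| Weeks 12 to 24, 24 to 36 | 12×7 = 84 | 84−10 = 74 to 84+10 = 94 | 70 (60 to 80) |
| Weeks 36 to 48 | 84 | 84−8 = 76 to 84+8 = 92 | 70 (62 to 78) |

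If Visit 1 is instead allowed its own ±5 days from Table 1, the first row becomes 18 to 38 days, with a delay of 4 to 24. The nominal figures do not change.

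Share of the Safety Period with 84-day spacing: (48 − 12)/48 = 36/48 = 75%.

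Every gap exceeds 14 days. Scheduled draws can therefore show persistence, but always after the limit has passed.

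**The case against.** The strongest reply is that the protocol does not leave a raised value unattended. Under Protocol 6.1.7.1 an abnormal laboratory value can be an adverse event, adverse events must be followed to an outcome, and the investigator is to order further tests as needed. Protocol 6.1.7.8 repeats the follow-up duty for serious and treatment-related events. Sections 3.3 and 3.4 let the investigator stop treatment or lower the dose. A criterion worded as lasting more than two weeks itself implies a recheck, and most investigators would make one. A laboratory manual, which I have not seen, might also specify reflex tests.

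Much of this stands. Follow-up is an obligation once the value is recorded as an adverse event. But recording a laboratory value rests partly on the investigator's judgment, and none of these sections names a test or an interval. The sponsor's review of medical decisions in Protocol 10.3 takes place before database lock, too late to protect a patient on treatment. The protocol does write conditional tests where it wants them: note c, urine microscopy ("If protein, occult blood, nitrite, or leukocyte esterase values are out of range a microscopic examination will be performed"), and hormone assays one month after a hormone dose change (4.7.1).

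Two stronger readings are tempting, and the documents support neither. A reader might infer that the liver rule cannot be applied, or that ALT/AST goes unmeasured. In fact ALT and AST are required at all seven scheduled draws and at early withdrawal, and most of the rule works at visits. A reader might also turn the 70-day delay into 140 further doses at two a day (70 × 2) and treat that as expected exposure. That is a worst case: the elevation must persist throughout, with no recheck and no dose stop. The protocol's summaries of the sponsor's own studies (1.3 and 1.3.3) give no rate of ALT/AST elevation, so the number affected among at most 66 patients cannot be estimated.

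**Conclusion.** The point holds in a limited form. INR is never a required or reflex test, so one branch of a mandatory criterion cannot trigger from required data; the patients for whom that branch alone matters are a narrow group. ALT/AST is measured, but no repeat is timed to the 2-week limit. Scheduled draws show persistence nominally 14 days late for values first seen at Day 1, Week 4 or Week 8, and 70 days late for those first seen at Week 12, 24 or 36.

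The delays assume a persisting elevation, no discretionary recheck and no dose stop. Confidence is high that the protocol and SAP are silent on both tests, and lower about what sites would do in practice. This is a cheap improvement to patient safety. It does not affect the validity of the planned summaries.

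**What to change.** Add one footnote to Protocol Table 1 in the style of note c, with matching text in 3.5 and 6.1.4:

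- After any ALT or AST above 3x ULN, draw INR promptly, and total bilirubin if it was not in the same sample.
- After any ALT or AST above 5x ULN, repeat ALT/AST early and again just after day 14.

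The sponsor should set the exact intervals, since the documents give none. As an illustration, a repeat on day 15 would show persistence 15 − 14 = 1 day past the limit, instead of 14 or 70.

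The cost is the added text and a few extra blood draws, only in patients with such elevations. That burden deserves mention in a study that enrolls children, but it is small. No new SAP table is needed: SAP 6.7.3.1 already provides for listing any additional analyte received, which would cover INR.

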4. TREATMENTS

4.1. Treatments Administered

Patients or parent/caregiver will be reminded how to measure, take their dose, and record their dose in the dosing diary when the IP is dispensed for the first time.

Total daily doses between 20 mg/kg/day, 30 mg/kg/day, and 40 mg/kg/day will be administered with standard meal, in two equivalent daily doses approximately every 12 hours.

4.2. Identity of Investigational Product

The active pharmaceutical ingredient (API) in Cannabidiol Oral Solution is a pharmaceutical grade synthetic CBD manufactured according to cGMP. It is an off-white to pale yellow resin or crystal substance that is soluble in several organic solvents with an acid dissociation constant (pKa) of 9.64. The solution is a clear, colorless to pale yellow-brown colored solution (CBD concentration of 100 mg/mL) filled into a 30 mL amber glass vial. More detailed information may be found in the IB.

4.3. Selection of Doses in the Study

Patients total daily dose will ranging from 20 mg/kg/day, 30 mg/kg/day, and 40 mg/kg/day. Doses of CBD may be adjusted at the investigator's discretion up to a maximum of 40 mg/kg/day. Doses greater than 40 mg/kg/day are not allowed

4.4. Selection and Timing of Dose for Each Patient

Once the informed consent for INS011-17-115 is provided, patients will initiate this long-term safety study. Total daily dose will range from 20 mg/kg/day, 30 mg/kg/day, and 40 mg/kg/day.

Patients will take each dose approximately every 12 hours with standard meal in order to ensure consistent plasma levels are achieved. The date and time of all investigational product administrations will be documented in the case report form (CRF).

4.5. Blinding and Unblinding Treatment Assignment

Not applicable. This is an open-label study.

4.6. Treatment Compliance

The prescribed dosage, timing, and mode of administration of IP may not be changed except as directed by the investigator.

The investigator, a member of the investigational staff, or a hospital pharmacist must maintain an adequate record of the receipt and distribution of all study medication using the Drug Accountability Form. These forms must be available for inspection at any time.

All supplies of IP should be accounted for at the termination of the study and a written explanation provided for discrepancies. All used and unused supplies, and packaging materials are to be inventoried and returned to the Sponsor or a designee by the investigator. The

investigator is not permitted to return or destroy unused clinical drug supplies or packaging materials unless authorized by the Sponsor or a designee.

If the study is terminated, discontinued, suspended, or completed, all used and unused supplies of the investigational product may be destroyed via the use of a third-party vendor or be returned to the Sponsor or a designee after the final drug accountability check has been performed. A certificate of destruction will be provided to the Sponsor.

All regulations issued by the DEA concerning the accountability of Schedule I medications will be followed (e.g., prevention of diversion).

4.7. Permitted and Prohibited Therapies

4.7.1. Permitted Therapies

Any medications (other than those excluded by the protocol, see Section 4.7.2) that the investigator considers necessary for a patient's welfare and will not interfere with the investigational product may be administered at the investigator's discretion.

Growth hormone, thyroid hormone, and psychotropic medications are permitted, provided they meet the stability requirements described in the inclusion criteria.

Adjustments to growth hormone and thyroid hormone medications are permitted as needed based on weight. Laboratory assessments for IGF-1/BP3 are required one month after any changes to growth hormone medication, and assessments for FT4 and TSH are required one month after any changes to thyroid hormone medication. No changes to psychotropic medications are allowed.

4.7.2. Prohibited Therapies

During the Safety, Taper, and Follow-up Periods, patients are not to receive the following:

- Any cannabinoids other than study medication (CBD, Δ^9 -THC, hemp oil, Realm Oil or marijuana).
- Felbamate.
- Use of weight loss agents or drugs known to affect appetite (including glucagon-like peptide-1[GLP-1] analogs).
- Any other investigational drug or investigational device.
- Medication that are strong inhibitors/inducers/ sensitive substrates with a narrow therapeutic index for P450 3A4 (CYP3A4), CYP2D6, CYP3A4, or CYP2D6.

Although they are not prohibited, patients taking concomitant medications may require that the patient is monitored with special care to identify any AEs arising due to the potential for altered drug metabolism.

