1.1.2. Metabolism and Potential Drug Interactions

The major biotransformation pathway for CBD is similar to that of other cannabinoids and mediated by hydroxylation by cytochrome P450 (CYP) proteins (Harvey et al., 1991). Cannabidiol is metabolized primarily in the liver by CYP3A4 and to a lesser extent by CYP2C19.

Its interactions with human drug metabolizing enzymes (as a substrate, inhibitor, or inducer) were recently reviewed (Stout and Cimino, 2014; Bergamaschi et al, 2011b). Specifically, CBD inhibits CYP3A4, CYP3A5, CYP2D6, and CYP1A1 in vitro (Johannessen and Landmark, 2010; Yamaori et al., 2010, 2011a, 2011b;). It also appears to inhibit CYP2C9 (Yamaori et al., 2012) and the transport protein P-glycoprotein (Holland et al., 2006; Zhu et al., 2006).

Further details may be found in the Investigator's Brochure (IB).

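### The prohibited-drug bullet in Protocol 4.7.2 lists CYP3A4 and CYP2D6 twice each and omits CYP2C19, which Section 1.6 names as a predominant CBD enzyme

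*Protocol*

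**What the plan says.** The last bullet of Protocol Section 4.7.2 prohibits, through the Safety, Taper and Follow-up Periods, strong inhibitors, strong inducers and "sensitive substrates with a narrow therapeutic index for P450 3A4 (CYP3A4), CYP2D6, CYP3A4, or CYP2D6". The section then closes with a general sentence that names no enzyme: "Although they are not prohibited, patients taking concomitant medications may require that the patient is monitored with special care".

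Section 1.6 lists CYP interaction among the potential concerns with CBD and states: "Cannabidiol is metabolized predominantly by CYP3A4 and CYP 2C19. Cannabidiol may inhibit these two isozymes, as well as having small effects on CYP3A5, CYP2D6", with CYP1A1 and CYP2C9 also in the small-effects group. It then names the safeguards. Alongside the eligibility criteria, the "concomitant medication guidelines, and safety monitoring (AEs, clinical laboratory, vital signs, ECG, and physical examination assessments) planned for this study are intended to minimize" these risks.

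Section 1.1.2 is weaker on CYP2C19. On metabolism it says: "Cannabidiol is metabolized primarily in the liver by CYP3A4 and to a lesser extent by CYP2C19". On inhibition it says: "Specifically, CBD inhibits CYP3A4, CYP3A5, CYP2D6, and CYP1A1 in vitro". It adds CYP2C9 and P-glycoprotein, does not list CYP2C19 as inhibited, and refers to the Investigator's Brochure for detail.

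Section 4.7.1 allows any non-excluded medication that the investigator considers necessary for the patient's "welfare and will not interfere with the investigational product may be administered" at the investigator's discretion. It also says: "No changes to psychotropic medications are allowed". Section 6.1.7.9 asks sites to monitor with special care patients whose other drugs are metabolised by any of several enzymes, CYP2C19 among them.

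**The concern.** A list of four entries that holds two distinct enzymes needs correcting whatever was meant. The missing enzyme is one that Section 1.6 ranks with CYP3A4 both for metabolising CBD and for being inhibited by it. CYP2D6, by contrast, is fully covered by the ban, although Section 1.6 credits CBD with only small effects on it and neither 1.1.2 nor 1.6 says that it metabolises CBD. No reason is given for treating the two enzymes this way round.

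What is at stake is how well a stated safeguard works. Sites have a firm rule in advance for CYP3A4 and CYP2D6 drugs. For CYP2C19 drugs they have case-by-case judgement and monitoring. The entry rules in Section 3.2.1 limit the exposure: psychotropics and growth hormone must have been stable during INS011-16-085, and other treatment stable before entry. They do not stop a new non-psychotropic drug from being started under 4.7.1 during the 48 weeks of treatment.

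**Working it through.** The plan states no figure to reproduce. The check sets the sections side by side.

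| Enzyme | 1.1.2: metabolises CBD | 1.1.2: inhibited by CBD | 1.6: metabolises CBD | 1.6: effect of CBD | Entries in 4.7.2 bullet | 6.1.7.9 monitoring |
|---|---|---|---|---|---|---|
| CYP3A4 | primary | yes, in vitro | predominant | may inhibit | 2 | substrates |
| CYP2C19 | lesser extent | not listed | predominant | may inhibit | 0 | substrates |
| CYP2D6 | not named | yes, in vitro | not named | small | 2 | substrates |
| CYP2C9 | not named | appears so | not named | small | 0 | substrates |

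**Count of entries.** CYP3A4 2 + CYP2D6 2 = 4 entries, 2 distinct enzymes, CYP2C19 none. Nothing else in the protocol or SAP bars CYP2C19 drugs as a class.

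**Count by drug type.** The bullet covers three types: strong inhibitor, strong inducer, and sensitive substrate with a narrow therapeutic index. Barred by name: CYP3A4 3 of 3, CYP2D6 3 of 3, CYP2C19 0 of 3. Monitored with CYP2C19 named: 1 of 3 (substrates, in 6.1.7.9). These counts describe the wording; they do not measure risk.

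**What remains for CYP2C19, by direction of the interaction.**

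1. Another drug changes CBD exposure (strong inhibitors and inducers). The non-interference condition in 4.7.1 applies, by investigator judgement, together with the general sentence in 4.7.2. Section 6.1.7.9 does not reach these drugs, because it is limited to drugs that the enzyme metabolises.
2. CBD changes the other drug's exposure (substrates). Section 6.1.7.9 applies, with the same general sentence. The condition in 4.7.1 does not, as worded, because it concerns interference with the investigational product and not the reverse.

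**Internal consistency.** Section 6.1.7.9 derives its list from CBD's inhibition of drug metabolism and cites 1.1.2 for it, yet 1.1.2 does not list CYP2C19 as inhibited. On this point 6.1.7.9 agrees with 1.6. The protocol therefore needs one settled statement on CYP2C19, whichever way the ban is decided.

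**The case against.** The strongest reply is that the text can be read as two tiers: bar two enzymes and monitor a wider set. Section 6.1.7.9 names CYP2C19 with CYP2C9, CYP1A2 and P-glycoprotein, and those three are also monitored without being barred. Section 1.1.2, the dedicated metabolism section, ranks CYP2C19 below CYP3A4. Other controls also exist: dose reduction or withdrawal for poor tolerability (3.4), liver stopping rules (3.5), and laboratory tests and ECG at every Safety Period visit. Much of this stands. The two-tier reading is possible, and these controls would limit harm after an effect appears. They do not explain the repeated entries, and no control beyond judgement and a general sentence addresses strong CYP2C19 inhibitors and inducers.

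Four stronger readings are tempting and are not supported:

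- A reader might infer that the repeats prove CYP2C19 was dropped by mistake. They could equally come from merging two lists for the same two enzymes; the documents do not show which.
- A reader might infer that CYP2D6 does not belong in the ban. Section 1.1.2 lists it as inhibited by CBD in vitro, so its place is reasonable.
- A reader might infer that every CYP2C19 drug should be barred outright. For a rollover patient on a stable CYP2C19 psychotropic, that would clash with 4.7.1, which permits the drug and forbids changing it.
- A reader might size the gap from the reciprocal clobazam interaction in Section 1.3 or from the spacing of visits. The documents do not attribute the clobazam interaction to CYP2C19, and the visit schedule is the same for every drug and would not change with the fix.

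**Conclusion.** The point holds as a modest correction to conduct and patient safety. The bullet is defective on its face, and it leaves out an enzyme that Section 1.6 treats as one of the two main ones while relying on the concomitant medication rules to contain the risk. It is not an analysis problem: no estimate, test or table is shown to be affected, and a reader should not infer bias in the safety summaries from it.

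The size is limited to the wording: 0 of 3 drug types barred by name for CYP2C19, against 3 of 3 for each listed enzyme. The documents give neither the magnitude of a CYP2C19 interaction nor the number of patients on such drugs. If no patient takes one, nothing changes. The conclusion gives weight to Section 1.6, which 6.1.7.9 supports, over the weaker wording in 1.1.2. The Investigator's Brochure, to which 1.1.2 defers, may settle that difference.

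**What to change.** Replace the bullet in Section 4.7.2 with:

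> Strong inhibitors or inducers, or sensitive substrates with a narrow therapeutic index, of CYP3A4 or CYP2D6; and no new start of such drugs for CYP2C19 during the study. Patients already on a stable CYP2C19 drug at entry may continue it with the special-care monitoring in 6.1.7.9.

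Extend Section 6.1.7.9 to strong CYP2C19 inhibitors and inducers, so that the continuing patients are covered in both directions. Reconcile Section 1.1.2 with Section 1.6 on the role of CYP2C19. If CYP2C19 was left out on purpose, delete the repeated entries and state why monitoring is enough.

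The existing CYP3A4 and CYP2D6 bans stay in full, and the provision for stable drugs avoids the conflict with 4.7.1. The cost is a short protocol amendment with IRB approval. The clinical downside is that a patient who newly needs such a CYP2C19 drug must use an alternative or stop CBD. The SAP needs no new analysis or table.
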